2.9.2. Timepoints for assessments

Quantitative outcome data will be collected at three timepoints. At baseline (T0), at midline 6 months post baseline (T1), and at endline 12 months post baseline (T2; primary time point for between-group comparisons). T1 assessments consist of adolescent surveys only (i.e. no caregivers), and will only include MMAPP, DBIS, Stirling and Hope. Implementation of services in the experimental arm will be introduced after baseline assessments are completed and will run

throughout the academic year (three terms). Service delivery will be ongoing for the entire study period to ensure a pragmatic implementation approach and ensure the evaluation of population-level outcomes (which requires for some of the experimental arm participants to not receive services between measurement points). At T1 and T2 we will attempt to follow-up all participants enrolled at baseline, also those that have left school in the meantime. Data collection will follow this schedule:

Baseline evaluation study (T0)	Start June 2025	Period
Implementation services	Start July – November 2025	Terms 2 and 3
Midline evaluation study (T1)	Start December 2025	
Continued implementation	January/February – April	Term 3
_	(2026)	
Endline evaluation study (T2)	May (2026)	

2.9.3. Data management

The War Child Alliance Research and Development Data Management Policy serves as guidance on all data management and data sharing issues (policy available upon request). Names and phone numbers obtained on the consent forms will be kept in locked cabinets in locked offices or encrypted and password protected in the case they are stored digitally. Quantitative data. All data obtained via ODK will be anonymized using participant ID numbers during data collection and when exported for analysis and storage. To further improve the quality of data collected, the study scientific coordinator will conduct routine data checks and follow up to check for any inconsistencies and missing data in the database. Any errors identified in the data collected will be sent to the research assistant teams for correction. Statistical monitoring will also be implemented to look at variables for which distributions differ from the rest of the observed data, to highlight systematic (non-random) faults in filling the case registration forms and logbooks, compliance, SAEs, and to guide targeted monitoring. Comparison of distributions is made by statistical tests or models.

At the end of the data collection exercise, a final data review will be conducted by the coinvestigators and lead statistician, and the remaining data issues will be adjudicated. The paper data files will be collected from the field offices monthly and stored in a locked cabinet in the War Child Uganda office. Qualitative data. The study scientific coordinator will upload any qualitative data, including audio files, on a password encrypted secure data server of the Research and Development Department of War Child Alliance. The server will be password protected and accessed from password protected and encrypted laptops. Data security. Data entered electronically will be backed-up securely and password protected and encrypted. Any queries identified will be resolved promptly by the trial management team. Data entered on the server will only be available to the War Child Alliance research team. Any external partner or parties who require access to the data will only have access once a data sharing agreement has been signed, in which the party agrees to abide by the War child Alliance Data Management Policy. Paper copies of informed consent forms (i.e., signed release of information forms) and data files will be collected from the field offices monthly and be stored securely in the locked cabinet in the War Child Uganda office. Length of data retention, archiving conditions and management. Both qualitative and quantitative data will be stored for a period of at least 7 years after completion of the study. Any modification or deletion of data will be granted via the standard authentication and access-control features. Data ownership and sharing. War Child Alliance has, in all cases, ownership of the research data.

2.9.4. Contamination and drifting

To assess the extent of contamination across trial arms, participants in both arms will be asked several structured questions at each of the measurement points (excluding baseline) about the extent to which they shared information and materials about the intervention received with others in the community (experimental arm), and whether they have heard of information or materials about the intervention from others. This information will be used descriptively to assess the level of contamination and drifting.

2.9.5. *Masking*

Research assistants and lead investigators (i.e. all named investigators on this protocol, including the lead statistician) will remain masked to allocation status of participants enrolled into the study – except the Scientific Coordinator, as it will be impossible to remain masked while coordinating all field operations. A Standard Operating Procedure (SOP) will be put in place with details on who can know what, on what scripts can be used when communicating about the study and what strategies are in place to prevent and assess unmasking. The main strategies to maintain masking will be (1) working with separate research assistants for qualitative and quantitative assessments; (2) having separate convening places for research assistants and intervention facilitators, as part of a larger strategy to avoid contact between both groups; (3) research assistants will also prompt participants (adolescents and caregivers) not to share any information on the type of services that

they receive. The level of (un)masking will be assessed at the end of each of the three time-points assessments.

2.10. Analyses

2.10.1. Effectiveness analyses [RQ1]

Primary comparison: (i) Baseline-to-endline comparison on MMAPP total score and (ii) baseline-to-endline comparison on Stirling total score.

Secondary comparisons: (iii) Baseline-to-endline comparison on all secondary, indirect and mediating outcomes; (iv) Baseline-to-midline on all outcomes; (v) Midline-to-endline on all outcomes. The analysis will follow an intention-to-treat approach, analyzing all participants based on their random assignment to the trial arms. Preliminary analysis will compare baseline characteristics to assess successful randomization across trial arms. Multilevel mixed-effect linear or logistic regression models (depending on outcome) will be employed for all primary, secondary, mediation, and indirect outcomes, treating the intervention group as a fixed effect. These models will account for the hierarchical structure of the data, with children nested within schools. Demographic variables and baseline outcome measures will be included as covariates. Additionally, (vi) we will evaluate mediation effects of social connectedness, hope and family functioning; (vii) Separate models will estimate differences between trial arms at the 6-month midline and 12-month endline, with distinct sub-group analyses for boys and girls; (viii) sensitivity analyses will be conducted wherein siblings are excluded; and (ix) analyses of the relative contribution of interventions or combination of interventions to change in the primary outcomes. A detailed Statistical Analyses Plan (SAP) will be developed and will be made publicly available before the end of the last data collection has been completed.

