2. METHODS

[figure not shown]
2.1.Design

The primary study design [RQ1] will be a pragmatic parallel two-arm cluster Randomized Controlled Trial (cRCT), randomizing 18 zones (i.e. clusters; a zone is an administrative unit in Uganda) in a 1:1 ratio (stratified for school size) to one of the two study arms (see Figure 1). The two arms are the multi-component mental health care system (experimental arm) vs waitlist control. A random population sample of children (age 11-16) will be drawn from schools (one school per cluster) from the selected zones and follow-up 6 and 12 months later, wherein the type and extent of services received by children in the experimental arm is not a priori defined following a naturalistic service delivery framework (i.e. not all children and their caregivers will participate in the interventions, further explained below). This means that some children and their caregivers that are part of the experimental arm will not receive any service, and other children and their caregivers receive all available services that are part of the care system (see further details under 'Sample' below). Furthermore, children and their caregivers that are not part of the

study sample but are part of the enrolled schools in the experimental arm may also receive any or all the services being offered in the care system. This means that children that have been recruited into the study may benefit from the mental health care system either directly (i.e. receiving services) and/or indirectly (i.e. through peers and caregivers receiving services).

The rationale for this approach is to be able to assess the *population-level*² effect of a mental health care system, rather than a *participant-level effect*. Given the pragmatic implementation, intention-to-treat will be our primary analysis framework. A cRCT was selected because of the potential contamination of the implementation of a multi-component mental health care system that involves children, their caregivers and school-personnel. (*See Figure 1 for study flowchart*).

Figure 1. Flowchart

Note: All T0 and T2 assessments include children and their caregivers, T1 consists of a shortened version of the adolescent surveys only.

[figure not shown]

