2.8.3. Sample size calculation

[figure not shown]
This cRCT was designed to have at least 80% power to detect a moderate effect size of Cohen's d = 0.30 for the primary outcome (MMAPP) at the primary time point (endline). Assumptions were the following: intra-cluster correlation coefficient (ICC) due to clustering by zone/school of 0.04 (based on population level data from two systematic reviews on ICCs [Shackleton et al, 2016; Parker et al, 2023]), 2-tailed 5% significance level, resulting in an estimation of 18 clusters (9 per arm) and n=176 children per cluster. Adjusted for a loss to follow-up rate of 30% makes the total sample size n=4536 (across study arms) – translating to n=252 per school. The LTFU

rate is a somewhat conservative estimate, as we will attempt to follow-up all participants enrolled at baseline, even if they leave school. We will not adjust for household level clustering (as siblings are included) in the analyses, and therefore this has not been included in the sample size calculations.

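### The endline effect is to come from a separate model that makes no use of midline scores for children missing at endline, and separate boys' and girls' analyses do not test whether the effect differs by sex

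*Protocol*

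**What the plan says.** Section 2.10.1 specifies multilevel mixed models with children nested in schools, arm as a fixed effect, and demographic variables and the baseline outcome as covariates. Item (vii) adds: "Separate models will estimate differences between trial arms at the 6-month midline and 12-month endline, with distinct sub-group analyses for boys and girls". No level for visits within a child is named. The same section promises: "The analysis will follow an intention-to-treat approach, analyzing all participants based on their random assignment to the trial arms".

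Section 2.9.2 makes the 12-month visit (T2) the primary time point. The 6-month survey (T1) is limited to MMAPP, DBIS, Stirling and Hope, so both primary outcomes are measured at midline.

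Section 2.8.3 inflates the sample for 30% loss to follow-up and remarks that the "rate is a somewhat conservative estimate, as we will attempt to follow-up all participants enrolled at baseline, even if they leave school".

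On sex, section 2.8.2 draws boys and girls 1:1 within each school, and section 2.11.6 says data will be analysed by gender through subgroup analyses. No arm-by-sex interaction is mentioned. The protocol states no method for missing outcomes and defers detail to a later SAP.

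**The concern.** With one outcome per child per model, a child who gives a midline score and is then lost contributes nothing to the endline contrast unless the endline score is imputed. That midline score is probably the best available predictor of the missing value, and the trial will already have collected it.

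This matters for bias as well as precision. A baseline-adjusted model fitted to observed endline scores is sound if loss depends only on baseline scores and covariates. If loss also depends on midline distress, and does so differently by arm, the estimate of the primary effect is biased. The arms do differ in a process that might create such a difference: case detection with ReachNow and referral to EASE run in the experimental arm only during the trial year.

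On sex, two separate analyses invite a comparison of two p-values. That comparison is not a test of whether the effect differs, and discordant results are common when the true effects are identical.

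**Working it through.** **1. The plan's own figures.** Inputs from section 2.8.3: d = 0.30, ICC = 0.04, two-sided 5%, 9 clusters per arm, 176 analysable children per cluster, 30% loss.

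- Design effect = 1 + (176 − 1) × 0.04 = 8.0.
- Effective children per arm = 9 × 176 / 8.0 = 198.
- Noncentrality = 0.30 / √(2/198) = 2.985. With a t distribution on 16 df, power is 0.8001, and 176 is the smallest cluster size that reaches 80%.
- Enrolment: 176 / 0.70 = 251.4, rounded up to 252 per school; 252 × 18 = 4536.

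The stated sample size reproduces exactly.

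**2. Children without an endline score at the planned loss.** 18 × 176 = 3168 analysable, so 4536 − 3168 = 1368 have no T2 score. (30% of 4536 is 1361; the difference is rounding.) This is an upper figure for what midline scores could help with, because children lost before T1 have none.

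**3. Size of possible bias.** The protocol gives no correlations, midline effect or dropout mechanism, so all of the following are assumptions: true T2 effect 0.30 SD, T1 effect 0.15 SD, 30% loss in each arm depending on the T1 score through a logistic model. The simulations are large and at individual level, without clustering. The baseline-adjusted T2 model on observed scores is compared with the same model after arm-specific imputation of T2 from T0 and T1.

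Set B has correlations T0–T1 0.50, T0–T2 0.45, T1–T2 0.60:

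| Log-odds slope of loss per SD of T1 distress | Endline only | Using T1 |
|---|---|---|
| Same in both arms (0 to 1) | 0.294 to 0.303 | 0.295 to 0.301 |
| Control only, 0.5 | 0.247 | 0.300 |
| Control only, 1.0 | 0.209 | 0.307 |
| Opposite signs, 0.5 each | 0.188 | 0.298 |

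Set A has correlations 0.6, 0.5 and 0.7 in the same order. Control-only slopes of 0.5 and 0.7 (odds ratios e^0.5 = 1.65 and e^0.7 = 2.01) give 0.242 and 0.224 from the endline-only model, and 0.299 and 0.302 when T1 is used. At slope 0.5 the shrinkage is (0.30 − 0.242) / 0.30 = 19%.

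**4. Sex.** Each sex has 88 analysable children per school.

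- Design effect = 1 + 87 × 0.04 = 4.48; effective n per arm = 9 × 88 / 4.48 = 176.8; power for d = 0.30 on 16 df is about 75%.
- With equal true effects of 0.30 in both sexes, simulation gives one sex significant and the other not in roughly 17% of trials when the within-school correlation between the sexes' school effects is 1.0, rising to about 30% when it is 0.5. That correlation is assumed.
- An interaction test is feasible. With four arm-by-sex cells of 9 × 88 = 792 and no cluster-by-sex variance (assumed), its SE is √(4 × 0.96 / 792) = 0.070 SD, and the difference detectable with 80% power is about 2.8 × 0.070 = 0.20 SD.

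**The case against.** The strongest reply is that the text contains no complete-case rule. Section 2.10.1 is silent on missing outcomes and defers to a SAP. Multiple imputation using T1 scores would fit separate models, a baseline covariate and the inclusion of all participants. This stands. A reader might infer that the plan drops 30% of the children and contradicts its own intention-to-treat statement. The documents do not support that: there is a tension, which the SAP could resolve. The 30% is also a planning figure that the protocol regards as somewhat conservative, with school leavers followed up.

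Item (vii) can also be read as an additional analysis rather than the primary one. That helps little, since the main model names only children within schools.

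A baseline-adjusted analysis at the primary time point is a standard method, and bias arises only under a differential mechanism. This stands too. Section 2.4 places the same referral pathway and case management in all 18 schools, and nothing in the documents shows that loss will depend on distress differently by arm. The simulations let T1 drive the whole 30% and ignore clustering. They illustrate direction and size, and do not show how a full mixed model performs with 18 clusters.

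One might also read the midline-to-endline comparison, item (v), as adjusting for a post-randomisation score. Section 2.10.1 does not say so; it names only baseline outcomes as covariates.

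Finally, the protocol nowhere claims that the subgroup analyses will show a sex difference. The point on sex is therefore a limit on interpretation, not an error.

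**Conclusion.** The point holds in a limited form. The protocol fixes separate midline and endline models without a visit level, so as written the primary T2 estimate leaves unused the midline scores of children who are later missing. At the planned loss, up to about 1368 of 4536 children lack a T2 score. The effect on the estimate is conditional: none of note if loss relates to midline distress in the same way in both arms, and a fall from 0.30 to about 0.24 SD if it does so in control only with a log-odds slope of 0.5. Stronger or opposite slopes bring it to about 0.19–0.22. These sizes rest on assumed correlations and on loss that is ignorable given T0 and T1. A trial with 80% power at exactly 0.30 has little room for such shrinkage, and the remedy uses data already planned.

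Separate boys' and girls' estimates are legitimate, but alone they cannot say whether the effect differs.

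**What to change.** For the four outcomes measured at T1 (MMAPP, DBIS, Stirling, Hope), replace the separate models in item (vii) with one of two options:

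- One longitudinal mixed model per outcome, with arm-by-time effects and random effects for school and child. The T2 contrast is primary. The T1 contrast and the T2-minus-T1 contrast come from the same model and serve items (iv) and (v), which are possible only for these outcomes.
- The baseline-adjusted T2 model, kept as it is, with multiple imputation that includes T1 scores and respects arm and school.

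State the choice in the SAP before endline data collection is complete, and align section 2.10.1 with it. Report an arm-by-sex interaction with its confidence interval next to the sex-specific estimates, and base any statement about a sex difference on the interaction.

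The cost is revised wording and slightly more complex modelling. No new data or visits are needed.

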The overall aim of the study is to evaluate the impact of a mental health care system on improving population level mental health of children in refugee settlements, with the following guiding research questions and hypotheses:

Research questions (RQ) and hypothesis

[RQ1] What is the population-level effectiveness of a multi-level multi-component care system on improving the wellbeing amongst adolescents (aged 11-16), and/or reducing depression, anxiety and externalizing symptoms amongst adolescents (aged 11-16 years) with elevated levels of emotional distress?

¹ A separate protocol will be developed and submitted describing a study that will be embedded within the main trial to evaluate how a care system performs in a real-world context (e.g. care pathways, quality of care, coverage etc.)

Hypothesis: Children in the experimental arm (i.e. mental health care system) regardless of whether and what services they received will have a greater improvement in wellbeing and/or reduction in depression, anxiety and internalizing symptoms amongst those with elevated levels at baseline, over a period of 12 months compared with children in the control arm (i.e. waitlist control).

[*RQ2*] What are the synergistic and indirect effects of a multi-level and multi-component care system and the associated cost-benefits?

Objectives: (i) Improve understanding of whether and what combination of interventions result in better mental health outcomes (i.e. relative contribution to outcomes by different component parts) – amongst the group of children receiving services; (ii) Improve understanding of the indirect effects of a mental health care system approach on other life domains, i.e. to what extent does the mental health care system result in effects beyond the intended (mental health) outcomes (i.e. school outcomes, bullying victimization or perpetration, domestic (parental) or intimate partner violence victimization or perpetration, risky sexual behavior, illegal substance use, child labor, early marriage). (iii) Improve understanding of the population-level cost-effectiveness of the mental health care system.

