Embedded sub-studies to evaluate synergistic effects, indirect effects, and cost-effectiveness [RQ2]. First, through a surveillance design we will track which children, and their caregivers get which services at what point in time throughout the implementation period (1 school year). This allows for analyses of a sub-sample of the cRCT that receives any of the interventions to investigate whether different combinations of interventions result in different outcomes. Second,

² Population level in this protocol refers to 'population of school-going children'.

the cRCT study will allow for secondary analyses to investigate the degree by which participants in the experimental arm show benefits in other outcomes related to schooling and child labor, violence, substance use, risky (sexual) behavior and early marriage. Third, we will also conduct an economic evaluation, in which we will examine costs and possible offsets of delivering the care system implementation and assess the cost-effectiveness of the program. The purpose will be to gather relevant information about the potential economic value of the interventions.

2.2.Setting

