Implementation model for the care system follows a pragmatic approach. This means that implementation is offered and implemented as it would be in a real-world context, rather than highly controlled (as would be the case in regular efficacy trials). Pragmatic implementation means that we accept close to real-world conditions and that we do not work with pre-set targets for participants (see also under sample below). In the case of the above-mentioned interventions, this means: First, within all enrolled schools all school personnel will be invited to participate in Community Tales workshops. Second, using schools as the entry point, TeamUp will be offered to P1-P6 school classes including children aged 11-16 over the period of 12 months. Importantly, planning of TeamUp will have two restrictions; (1) implementation will follow a randomized rotation system of classes to avoid bias of sequence, and (2) 10-20% randomly selected classes will be excluded from receiving TeamUp (because in real-world implementation contexts not all children can be reached by mental health interventions, yet we still want to evaluate the population-level effects, our design deliberately excludes classes from participation). TeamUp will be implemented as an extra-curricular activity, and participation for children is voluntary. Third, the caregiver support intervention, BeThere, is open to any caregiver with children between 3-16 years of age in the catchment area of the enrolled schools. Caregivers are recruited via information sessions that are held at school and the community-at-large about the availability and aims of BeThere. Fourth, ReachNow is implemented by TeamUp facilitators, as well as other selected community gatekeepers (i.e. trusted and respected members in the community). Selection of community gatekeepers (other than TeamUp facilitators) will be determined for each catchment area for each enrolled school, aiming for a rate of 1 trained gatekeeper per 3000 zone population. The number of gatekeepers per zone is dependent on the population size in the zone, our aim is to train 1 gatekeeper per 3000 residents. They include: Village Health Teams (VHTs), teachers, group activity facilitators, child protection committee members, local community leaders and refugee committee leaders. Specific inclusion criteria are: 18 years of age; trusted and respected members from the community; engaged in promoting child wellbeing; access to children, adolescents and caregivers; demonstrate high level of empathy and interest in children's wellbeing; willing to provide informed consent and participate in supervision meetings to provide feedback on feasibility of the approach; willing to sign and follow WCH's Child Safeguarding Policy, Code of Conduct and Code of Ethical conduct in using the CCDT. Upon detection of children in need of mental health care (of children in and out of schools), using the ReachNow tool, these children will be referred to Project Officers Psychosocial support (PO PSS)/case worker who will then refer to EASE facilitators (for children 11-16 years) and to external referral

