
[figure not shown]
basing on assessment of needs. Fifth, EASE will be offered to all children that get referred by TeamUp facilitators and community gatekeepers using the ReachNow tool. Furthermore, children can get referred to EASE from elsewhere (e.g. teachers, BeThere facilitators, health care volunteers), following a brief information session on the availability and aims of EASE. Sixth, EASE facilitators will be trained in referring children to subsequent specialized mental health care – when EASE is providing insufficient support, or when acute mental health problems arise (e.g. suicidality). Furthermore, EASE and TeamUp facilitators will refer children to child protection service in case of indications of severe maltreatment of abuse. See Annex 1 for an overview and example of the staffing per school to deliver the above-mentioned interventions over the course of a school year. See Table 1 below for an overview of who the different service providers are for each of the interventions, as well as details about the supervision.

Table 1: Characteristics of intervention facilitators and supervision

	Facilitators	Supervision
TeamUp	 Adults (non-mental health professionals) from the study context Selected through an open recruitment process Facilitators get remunerated per number of days worked. 	 Supervision is provided by the TeamUp Master Trainer (WCA staff), TeamUp Technical coach and PO-PSS (Facilitator). Group-based supervision takes place once per month Online/physical Community of Practice (COP)
ReachNow	 TeamUp facilitators (all) and community gatekeepers (e.g. teachers, community health volunteers) Community gatekeepers are selected through open recruitment process following these criteria: 1) At least 18 years of age; 2) Residing within the zones; 3) Trusted and respected members from the community; 4) Engaged in promoting child wellbeing; 5) No history of criminal record; 6) Able to write and read. No compensation is provided (facilitated on transport refund during meetings) 	- Supervision if provided by the ReachNow Master Trainer (WCA staff), Team Up trainer & PO-PSS Group-based supervision takes place once per 2 months

EASE	 Adults (non-mental health professionals) from the study context Selected through an open recruitment process Facilitators get remunerated monthly 	 Supervision if provided by the EASE Master Trainer (WCA staff), EASE trainer & partners Team Leader. Group-based supervision takes place once per month

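### Component contributions are to be judged only among children who receive services, while the random exclusion of classes from TeamUp is planned but never analysed

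*Protocol*

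**What the plan says.** RQ2 objective (i), in section 1.3, asks which combinations of interventions give better outcomes, "amongst the group of children receiving services". Section 2.1 repeats the restriction for the embedded sub-study: tracking services permits "analyses of a sub-sample of the cRCT that receives any of the interventions". Section 2.10.1 names the analysis in one line, "ix) analyses of the relative contribution of interventions or combination of interventions to change in the primary outcomes", without a comparator or model of its own.

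Section 2.3.1 sets out how children come to receive each component. TeamUp attendance is voluntary. BeThere is open to any caregiver in the catchment area with a child aged 3-16. For the third, "EASE will be offered to all children that get referred by TeamUp facilitators and community gatekeepers using the ReachNow tool"; other people may refer too.

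The same section contains two random elements. On order, "implementation will follow a randomized rotation system of classes to avoid bias of sequence". On coverage, "10-20% randomly selected classes will be excluded from receiving TeamUp"; the reason given is to imitate incomplete real-world reach, so that "our design deliberately excludes classes from participation". Neither element appears in the analyses of section 2.10.1 or in the sub-study text of section 2.1.

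**The concern.** A comparison of children by the services they happened to receive mixes the effect of a service with the reasons for receiving it. Children sent to EASE have been picked out as distressed. Children who attend TeamUp, and those whose caregivers attend BeThere, have chosen to or had it chosen for them. A ranking of components on this basis can reflect who was referred or willing rather than what helped.

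The restriction to recipients adds a second problem. A child in a randomly excluded class who receives nothing else is part of the randomised comparison group for TeamUp, and drops out of the analysis. So does a child in an offered class who attends nothing. Conditioning on receipt, which occurs after randomisation, breaks the one comparison of a component that chance has balanced.

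At stake is the answer to RQ2(i), which could guide decisions on which components to keep.

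**Working it through.** **1. The plan's own figure.** Section 2.8.3 gives d = 0.30, ICC 0.04, two-sided 5%, 9 clusters per arm and 176 analysable children per cluster.
- Design effect: 1 + (176 - 1) × 0.04 = 8.0.
- Power: 0.800 with a t distribution on 16 df (0.847 by normal approximation), so the stated size reproduces.
- Dropout: 176 / 0.70 = 251.4, rounded up to 252; 252 × 18 = 4536, as stated.

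The protocol gives no figure for the component analysis.

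**2. Bias in comparisons by receipt (illustration; all inputs assumed).** True severity is standard normal and no service has any effect. A child is referred if severity plus standard normal noise exceeds 1.8, which refers about 10%. Measurement reliability is 0.7, 0.8 or 0.9, and the correlation of true severity from baseline to endline is 0.5 or 0.7. The table shows referred minus not referred, in SD units, with higher meaning more symptoms.

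| Reliability | Correlation | Change score | Endline adjusted for measured baseline |
|---|---|---|---|
| 0.7 | 0.5 | -0.58 | +0.19 |
| 0.7 | 0.7 | -0.34 | +0.28 |
| 0.8 | 0.5 | -0.61 | +0.15 |
| 0.8 | 0.7 | -0.37 | +0.20 |
| 0.9 | 0.5 | -0.65 | +0.08 |
| 0.9 | 0.7 | -0.39 | +0.11 |

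Change scores show a benefit that does not exist, through regression to the mean. Baseline adjustment reverses the sign, because the measured baseline captures only part of what led to referral. Neither model removes the bias.

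**3. What the class randomisation could detect.** The experimental arm has 9 × 176 = 1584 analysable children. If all sit in classes that entered the TeamUp draw, 10% exclusion gives about 158 against 1426, and 20% gives about 317 against 1267. The number of classes per school (c) and the class ICC are not in the protocol, so I assume c = 6, 12 or 18 and ICC 0 to 0.10.

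Design effect DE = 1 + (176/c - 1) × ICC. SE = √(DE/n0 + DE/n1). Detectable effect at 80% power = (1.96 + 0.84) × SE.
- Best case, 20% excluded, ICC 0: SE 0.063, detectable 0.18 SD.
- 12 classes, 20% excluded, ICC 0 to 0.10: 0.18-0.27 SD.
- 12 classes, 10% excluded, ICC 0 to 0.10: 0.24-0.36 SD.
- 6 classes, 10% excluded, ICC 0.10: DE = 1 + (29.33 - 1) × 0.10 = 3.83, SE 0.164, detectable 0.46 SD, with 45% power for 0.30.

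The last case excludes only about 5 of 54 classes, where the normal approximation is optimistic. With whole classes (5 against 49, 29 children each) and a t distribution on 52 df:
- ICC 0.10: DE = 1 + 28 × 0.10 = 3.8; SE = √(3.8/145 + 3.8/1421) = 0.170; detectable 0.49 SD.
- ICC 0.02-0.04: detectable 0.31-0.36 SD.

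The range is therefore about 0.18-0.49 SD.

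**The case against.** The strongest reply is that item (ix) is a single line for an objective worded as improving understanding, with the method left to an SAP that is not shown. That is fair as far as it goes: the absence of an analysis by class assignment is established for the protocol only. But the recipient-only population is stated twice in the protocol, and an SAP that followed it would inherit the problem. The restriction can be corrected there; a baseline class that was never recorded may be harder to recover.

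Three stronger readings are tempting and are not supported.

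- A reader might infer that regression to the mean will be credited to EASE by a known amount. If recipients start 0.8 SD above the mean and the correlation is 0.5 (both assumed), the spurious improvement is 0.8 × (1 - 0.5) = 0.40 SD. That needs unadjusted change scores. Section 2.10.1 states baseline-adjusted models for the primary outcomes, and if these extend to (ix) the bias can run the other way.
- A reader might infer that the class comparison answers RQ2(i) for TeamUp at no cost. It estimates the effect of offering TeamUp to a class, not of receiving it. TeamUp facilitators also use ReachNow, so the offer includes any extra detection and referral. Sections 2.1 and 2.8.4 expect benefit through peers in the same school, which dilutes the contrast. It says nothing causal about EASE, BeThere or combinations.
- A reader might infer that early against late rotation at T1 gives a second clean test. Section 2.3.1 does not define rotation waves. A course of 24 weekly sessions barely fits, if at all, into July to November, about 22 weeks before T1, so the contrast would mostly compare partial with little or no delivery.

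**Conclusion.** The point holds in this limited form. The protocol confines the component question to children who receive services, where receipt is self-selected or follows detected distress. It leaves unused a random class assignment that supports a less biased comparison for one component. In the illustrative model the bias from referral is 0.34-0.65 SD towards benefit or 0.08-0.28 SD towards harm, depending on the analysis, so it can match or exceed the 0.30 SD design effect. These sizes rest on the assumed referral, reliability and stability values; only the change of sign is the general lesson.

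The class comparison would detect about 0.18-0.49 SD under assumed class numbers and ICCs. Precision is modest, and weakest if only 10% of classes are excluded. It would fall further if many sampled children are in classes outside the draw: TeamUp covers P1-P6, whereas section 2.8.2 samples by age with no limit on grade. The point concerns a sub-study question; the primary comparison between arms is unaffected.

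**What to change.** - Record for each sampled child in the experimental arm the baseline class, its random TeamUp assignment (offered or excluded) and its rotation slot. Keep the child in the baseline class throughout, because delivery runs into the next academic year.
- Add to item (ix) an intention-to-treat comparison at T2 of offered and excluded classes within experimental schools, limited to children in classes eligible for the TeamUp draw, with school effects, a class random effect and the baseline score.
- State that this estimates the effect of offering TeamUp, including its effect on ReachNow detection, and that spillover within schools dilutes it.
- Label all comparisons by services received, including those of EASE, BeThere and combinations, as exploratory and non-causal, and include baseline adjustment without presenting it as a cure.
- Treat early against late rotation at T1 as an optional exploratory contrast, only if the rotation waves support it.

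The cost is low: the allocation list kept in the trial dataset, a few variables per child and one further model. Sample size and the primary analysis do not change.
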